## 10 Statistical Considerations

### 10.1 Statistical design and procedures

Outcomes at each timepoint will be visually inspected for normality using histograms and qq-plots. If the data are deemed to be normal the hypotheses will be tested using a two-tailed, paired, student's t-test. Non-normal data will be tested using the Wilcoxon signed-rank test.

Acceptance criteria for the data, as applicable, is defined in Table 4 **Endpoints, test methods and hypotheses**. Subgroup analysis will not be performed as no subgroups are defined.

Repeated measures analysis has the advantage of increased power vis-à-vis group allocations and reduction in error variance associated with individual difference, as each subject acts as its own control. This is important for studying amputees as the group is a small proportion of the total population, and with specific inclusion/exclusion criteria the total eligible population becomes very small, making it difficult to find and recruit subjects to attain an acceptable level of power. This limited population pool often results in slightly heterogeneous sample, as the amputees available are few and far between, in every sense. Furthermore, no single amputation procedure and therefore amputated stump is exactly the same, making the experience of each amputee a bit unique. The within-subject design significantly reduces the individual differences when comparing the two conditions.

The drawback of the design is the potential of "carryover effects", i.e. experience from one condition can affect outcome or performance in the other condition, creating a confounding extraneous variable that varies with the independent variable. Such effects are: practice, positive carryover effect to the latter condition; and fatigue, negative carryover effect to the latter condition.

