**Table 4 Endpoints, test methods and hypotheses**

	Hypothesis	Test Method	Endpoint	Acceptance Criteria
A	Subjects reduced exertion performing 6MWT compared to previous prosthesis (primary outcome)	BORG scale	Mean difference in BORG score pre and post 6MWT compared to comparator	$H_0: \mu_1 \leq \mu_2$ $H_1: \mu_1 > \mu_2$ $p<0.05$
B	Subjects improved performance in 6MWT compared to previous prosthesis.	6MWT (meters)	Average distance walked in 6MWT compared to comparator	$H_0: \mu_1 \geq \mu_2$ $H_1: \mu_1 < \mu_2$ $p<0.05$
C	Subjects report on average no worse support in sit to stand and stand to sit than with previous prosthesis.	Self-report: PMQ (Questions 9 and 10) Likert scale 0-4	Total score of PMQ questions 9 and 10 compared to comparator	$H_0: \mu_1 \geq \mu_2 +  M_{NI} $ $H_1: \mu_1 < \mu_2 +  M_{NI} $ $ M_{NI}  = 1$ $p<0.05$
D	Subjects perceived safety in hill descent is no worse than with previous prosthesis.	Self-report: Modified PEQ 14F (rate your safety when walking down a steep hill using the prosthesis) Likert Scale 1-10	Average score compared to comparator	$H_0: \mu_1 \geq \mu_2 +  M_{NI} $ $H_1: \mu_1 < \mu_2 +  M_{NI} $ $ M_{NI}  = 1$ $p<0.05$
E	Subjects perceived safety in stair descent is no worse than with previous prosthesis.	Self-report: Modified PEQ 13D (rate your safety when walking downstairs using the prosthesis) Likert Scale 1-10	Average score compared to comparator	$H_0: \mu_1 \geq \mu_2 +  M_{NI} $ $H_1: \mu_1 < \mu_2 +  M_{NI} $ $ M_{NI}  = 1$ $p<0.05$
F	Subjects perceive no speed limitation while walking with the investigational device.	Self-report(yes/no): „Are you satisfied with your walking speed using your prosthesis/test prosthesis?”  Support question: “Do you feel that your walking speed is limited by your prosthesis/test prosthesis?”	Proportion of subjects (p) reporting satisfaction with walking speed on investigational device.	$H_0: p < 80\%$ $H_1: p \geq 80\%$ $p<0.05$

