## 8 Design of the Clinical Investigation

### 8.1 General

The test will be a two group prospective cross-over design, within subject comparison. Amputees are a small proportion of the general population. The population group specified in the inclusion/exclusion criteria is a further subsample of amputees. For practical reasons, i.e. to achieve statistical power, it is therefore more feasible to use within-subject comparison rather than creating study arms to compare. Furthermore, as mobile amputees generally have and use a prosthetic device for their daily activities, within-comparison is feasible comparing to the subject's previous device.

All investigational activities will be conducted at MCOP Silver Spring Prosthetic Clinic ([name]), Medical Center Boston, MA Prosthetic Clinic ([name]) and Motus Research ([name]).

As stated above the primary endpoint is the perceived exertion during walking measured by the Borg scale before and after 6MWT, see table 4, and the secondary endpoints are focused on the general mobility performance and efficacy of the investigational device, as well as performance of gait functions and ease of set up for average to highly active transfemoral/knee disarticulation amputees and CPOs. See previous chapter on objectives and hypothesis and Table 4 for rationale.

Drop-outs and withdrawals may be replaced if deemed necessary to fulfil the methodological standards of the study.

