### 10.2 Sample size calculation

Power analysis for the estimated required sample size was conducted using G\*Power. See protocol below:

t tests – Means:	Wilcoxon signed-rank test (matched pairs)
Options:	A.R.E. method
Analysis:	A priori: Compute required sample size
Input:	
Tail(s)	= One
Parent distribution	= Normal
Effect size dz	= 0.7084529
$\alpha$ err prob	= 0.05
Power (1- $\beta$ err prob)	= 0.8
Output:	
Noncentrality parameter $\delta$	= 2.6812808
Critical t	= 1.7676466
Df	= 13.3239449
Total sample size	= 15
Actual power	= 0.8150214

It is therefore expected that **at least 15** subjects are required to complete the protocol with a power of **0.8** and significance at **0.05**. Effect size was estimated for the primary endpoint based on a previous in-house study of the RHEO KNEE, a passive microprocessor controlled prosthetic knee.

Given a drop-out rate of **20%**, up to **18** subjects may be recruited.

For pass/fail criteria, see Table 4 **Endpoints, test methods and hypotheses**.

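### The primary test is two-tailed in section 10.1 but one-tailed in section 10.2 and one-sided in Table 4; at two-tailed 0.05 the named t-test has power 0.72 with 15 completers, not the stated 0.8

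*Combined protocol and SAP*

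**What the plan says.** Section 8.1 says that "the primary endpoint is the perceived exertion during walking measured by the Borg scale before and after 6MWT". This is hypothesis A in Table 4. Three places bear on how it is tested.

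- **Section 10.1 (analysis).** If the data look normal, "the hypotheses will be tested using a two-tailed, paired" Student's t-test. Otherwise, "Non-normal data will be tested using the Wilcoxon signed-rank test", with no sidedness given. The section then adds: "Acceptance criteria for the data, as applicable, is defined in Table 4".
- **Section 10.2 (sample size).** The G*Power listing is for a Wilcoxon signed-rank test with the tails entry set to one, alpha 0.05 and dz 0.7084529. It returns 15 subjects and an actual power of 0.8150214. The text concludes that at least 15 "subjects are required to complete the protocol with a power of" 0.8 at significance 0.05. It also says "Effect size was estimated for the primary endpoint based on a previous in-house study of the RHEO KNEE", and "For pass/fail criteria, see Table 4".
- **Table 4, hypothesis A.** The null is that the comparator mean is no greater than the investigational-device mean. The alternative is that it is greater. The criterion is p below 0.05.

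**The concern.** The only passage that names the analysis test makes it two-tailed. The only power calculation is one-tailed, and the hypothesis is directional. Table 4 gives a direction and a threshold but does not say which p-value is compared with the threshold. No passage supplies a bridge, such as halving the two-tailed p-value or using a two-tailed alpha of 0.10.

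Two things are at stake. First, if the Borg data are judged normal and section 10.1 is followed at 0.05, the stated power does not belong to the test that is run. Second, a favourable primary result with two-tailed p between 0.05 and 0.10 is a pass under Table 4 and section 10.2 but a fail under section 10.1. Section 10.3 requires sponsor approval and reporting of deviations from the statistical plan. Since either reading can be presented as the plan, that rule may not catch a choice made once the result is known.

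**Working it through.** **Inputs.** From section 10.2: dz = 0.7084529, alpha = 0.05, n = 15 completers, Wilcoxon by the asymptotic relative efficiency (A.R.E.) method with a normal parent distribution, for which A.R.E. = 3/π. Section 8.3 also requires at least 15 subjects to finish.

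**Formula.** Power is the probability that a noncentral t variable with df degrees of freedom and noncentrality δ exceeds the critical value. The two-tailed version adds the opposite tail, which is negligible here.

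**1. Reproduce section 10.2 (one-tailed Wilcoxon).**
- Effective n = 15 × 3/π = 14.3239, so df = 13.3239.
- δ = 0.7084529 × √14.3239 = 2.68128.
- One-tailed critical t = 1.76765.
- Power = 0.8150.

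All four match the listing. The arithmetic in section 10.2 is correct for a one-tailed test.

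**2. Change the sidedness, and use the test named in section 10.1.** For the paired t-test, df = 14 and δ = 0.7084529 × √15 = 2.74383.

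| Test, n = 15 | Critical t, one-tailed | Power | Critical t, two-tailed | Power | Difference |
|---|---|---|---|---|---|
| Paired t-test | 1.76131 | 0.832 | 2.14479 | 0.723 | 0.109 |
| Wilcoxon (A.R.E.) | 1.76765 | 0.815 | 2.15504 | 0.700 | 0.115 |

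The loss is about 0.11 on either test, so it comes from the sidedness and not from the move from Wilcoxon to t-test.

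**3. Effect needed for 80% power with 15 completers** (solved numerically).
- t-test: dz 0.675 one-tailed, 0.778 two-tailed.
- Wilcoxon: dz 0.693 one-tailed, 0.799 two-tailed.

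The planning value of 0.708 clears both one-tailed requirements and misses both two-tailed ones.

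**4. Results on which the two readings disagree.**
- t-test: the observed standardised mean difference must reach 1.76131/√15 = 0.455 one-sided, or 2.14479/√15 = 0.554 two-tailed. Values in between are disputed.
- Exact Wilcoxon, assuming 15 untied, non-zero differences, with W the unfavourable rank sum: P(W ≤ 30) = 0.0473 and P(W ≤ 31) = 0.0535, so the one-sided cut is 30. Twice P(W ≤ 25) = 0.0479 and twice P(W ≤ 26) = 0.0554, so the two-tailed cut is 25. Rank sums 26 to 30 are disputed (one-sided p 0.0277 to 0.0473; two-tailed p 0.0554 to 0.0946).
- The chance of landing in the disputed zone at the planning effect is the last column of the table: 0.109 or 0.115. Simulation of the exact Wilcoxon test with normal data (400,000 runs) gives power 0.810 and 0.700 and a zone of 0.1095.

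**5. Sensitivity.**
- Over assumed dz, t-test, n = 15: at 0.60, power is 0.714 one-tailed and 0.580 two-tailed (zone 0.13). At 0.80, it is 0.903 and 0.821 (zone 0.08).
- Over completers, two-tailed at the planning dz:

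| Completers | t-test | Wilcoxon (A.R.E.) |
|---|---|---|
| 14 | 0.689 | 0.665 |
| 15 | 0.723 | 0.700 |
| 16 | 0.755 | 0.732 |
| 17 | 0.783 | 0.761 |
| 18 | 0.809 | 0.788 |
| 19 | 0.831 | 0.812 |

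**The case against.** The strongest reply is that the plan already points to one-sided testing. Sections 10.1 and 10.2 both send the reader to Table 4, whose comparative hypotheses are all directional, and the non-inferiority ones are one-sided by construction. The sizing is one-tailed too. Against this stands one adjective in section 10.1, and correcting it leaves 15 completers and at least 0.8 power intact. This is the likeliest intention, and "two-tailed" does look like the outlier. But it does not settle the rule: a directional aim judged by a two-tailed p below 0.05 with the right sign is also coherent, and it is the only reading that uses the test as section 10.1 names it.

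Four further points qualify the finding.

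- **Error rate.** In the favourable direction the two-tailed rejection region lies inside the one-sided one, so choosing late cannot push the false-positive rate above 0.05. This stands. The ambiguity is between 0.025 and 0.05, and neither reading exceeds its own level.
- **Wilcoxon.** The direct contradiction concerns the t-test. For the Wilcoxon test, section 10.1 is silent and the only stated sidedness is one-tailed. This also stands.
- **Number of completers.** Up to 18 may be recruited, and 18 completers would give the two-tailed t-test 0.809. But at the plan's own 20% drop-out, 18 × 0.8 = 14.4, or about 14 to 15 completers and power 0.69 to 0.72.
- **Deviation rule.** Dropping an explicit "two-tailed" could be handled as a deviation under section 10.3. It could, but nothing in the text obliges anyone to treat it so.

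**Conclusion.** The concern holds. The plan gives the primary endpoint two incompatible pass/fail rules. The stated power of 0.8 belongs to a one-tailed test and not to the t-test that section 10.1 prescribes. With 15 completers and two-tailed alpha 0.05, that t-test has power 0.723; on the same test the one-tailed figure is 0.832. If the Wilcoxon test were also two-tailed, 0.815 would become 0.700. About 11% of trials at the planning effect (8% to 13% for dz from 0.80 to 0.60) would give a result that passes on one reading and fails on the other.

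The power figures depend on a dz taken from an in-house study of a different knee that the plan does not show. The rank-sum band assumes no ties or zeros, which may not hold for changes on a rating scale. The contradiction in the text depends on neither. No inflation of type I error is claimed.

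**What to change.** Before data are analysed, state one sidedness and one alpha for the primary endpoint, for both the t-test and the Wilcoxon test, in the same terms in section 10.1, section 10.2 and Table 4. Either of two versions would do.

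- **(a) One-sided 0.05.** Amend section 10.1 to match Table 4 and section 10.2. Fifteen completers stand, with power 0.83 (t-test) or 0.815 (Wilcoxon). The price is saying openly that the error rate in the favourable direction is 0.05 rather than 0.025.
- **(b) Two-tailed 0.05.** Keep section 10.1, extend it to the Wilcoxon test, say so in Table 4 for hypothesis A, and restate the power in section 10.2 as 0.72 (t-test) or 0.70 (Wilcoxon) for 15 completers. The price is a stated power below 0.8. If 0.8 is to be kept, 18 completers (t-test) or 19 (Wilcoxon) are needed.

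Unless the trial is resized under (b), this is a wording change with no extra patients, visits or data. Because section 10.1 applies "two-tailed" to the hypotheses in general, the same edit should state the sidedness of the other Table 4 rows, including the non-inferiority tests.

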**For all hypothesis:**

$\mu_1$  is average of measurements with comparator at 2 weeks;

$\mu_2$  is the average of measurements at 2 week follow up (investigational device);

$\mu_3$  is the average of measurements at 8 – 12 week follow up (investigational device);

and  $|M_{NI}|$  is the margin of non – inferiority

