## **8.2 Investigational Device(s) and Comparator(s)**

The investigational device is a powered microprocessor controlled prosthetic knee, with the same intended use as the previous version of the device (POWER KNEE II, a CE- marked device). See full details on the investigational device in **Clinical investigators brochure [3]**.

When the investigational device is on the market the device will be a single user device, with a typical use time of 5 years. Due to supply shortage, for clinical testing purposes the same investigational device may be used iteratively for periods of up to 3 weeks, maximum 3 times. Before refitting of a device, a reset to manufacturer settings will be performed as well as inspection for damage or malfunction. This supply shortage only refers to

visits 1 and 2 in the test procedure due to time limitations. For visit 3, investigational devices will be available for all users.

The subjects will be asked to use the investigational device as their primary prosthesis for **2-3** weeks. Individual exposure will differ between subjects. Subjects are expected to use the investigational device for their daily living activities as they would with any other prosthesis, for up to 18 hours a day depending on the individual. The comparator device will not be used within the timeframe of the intervention period of the study. Subjects will evaluate and provide feedback on their exposure of the comparator at baseline and prior to them being fitted to the investigational device or after, depending on the group they are assigned to. The investigational device is used with a smart app to adjust and interact with the knee. Össur Logic is an iOS smart app and it is required to adjust and interact with the knee. It is a standalone software as a medical device, used with other bionic devices as well, the app is documented separately, see **[1]**.

The comparator device is the users current prosthesis, it may be any passive MPK or a previous version of the Power Knee (AMPK), depending on the subject. Both have the same intended use and population as the investigational device.

The subject will be using the remaining part of their current prosthetic system with the investigational device, as it was used with the comparator device. If this is not possible, an advanced ESAR foot will be used and provided by Össur.

No other device, medication or intervention will be used. Aside from the Össur Logic app which is used to interact with the knee.

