#### Visit 1:

The subject will be consented and enrolled after verification of the inclusion/exclusion criteria. Potential risk of participating in the investigation will be explained to the subject.

The LPI will communicate to the study monitor the number of users he has identified that meet the inclusion criteria and are willing to participate.

Subjects will be randomized into 2 groups, using a random number generator. Half of the subjects (Group 1) will then be fitted with the investigational device. Prior to fitting the subjects of Group 1 will be asked to provide feedback on the current prosthesis, by filling in a set of questionnaires **and performing the AMPro, L-test and 6MWT with Borg scale**, to obtain baseline data. Subjects may be videotaped during fitting and while performing functional tests, care will be taken to blur out faces and other personally identifiable markers such as tattoos and birthmarks.

Users will be fitted within the standard methods of prosthetic fitting, alignment, introduction, training and walking on various terrain. After being fitted with the investigational device subjects will receive functional training on the investigational device prior to going home and using it as their usual prosthesis for approximately 2-3 weeks. They will be given an appointment for the follow up visit prior to leaving the testing site.

The other half (Group 2) will stay on their prescribed prosthesis until the next visit in 2-3 weeks.

CPO subjects will provide feedback on the ease of setup and fitting, they will also be videotaped during setup. Care will be taken to blur out faces and other personally identifiable markers such as tattoos and birthmarks.

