#### Visit 3:

During the third visit all subject will repeat the tests and questionnaires on the prosthesis they are fitted with. Subjects will have the option to use the investigational device for an additional 8-12 weeks, those who choose that will be fitted with the investigational device or stay on it, depending on which they are fitted with. They will be given an appointment for the fourth visit 8-12 weeks later. They will be contacted via telephone 4-5 weeks later and asked to provide feedback on their experience with the device so far, see script in **Appendix 18.1**. Those that choose not to keep using the investigational device will be fitted back on their prescribed prosthesis and end their participation in the study at visit 3.

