**iii) Measurements and data collection**

The same questionnaires, consisting of four valid instruments (PMQ, PEQ, PLUS-M, Borg) and in-house questions on the performance of the investigational device, will be used and filled in at three-four separate points in time. The same functional tests (L-test and 6MWT) will also be carried out at two points in time (except for those that elect the optional 8-12 week follow up period, there will be an addition visit with data collection and a follow up phone interview), the AMPRO will be performed at baseline to verify users K-level. The activity report will be generated from the Investigational device software application. See Table 6 for visit schedule and study procedures. **Table 6 Visit schedule and procedures**

Procedure/activity	Recruitment phase: 2-6 weeks prior to baseline	Group 1 visit 1: Baseline	Group 2 visit 1: Baseline	Group 1 visit 2: 2/3w F/U	Group 2 visit 2: 2/3w F/U	Group 1 visit 3: 4/6w F/U	Group 2 visit 3: 4/6w F/U	Visit 4 Optional 8-12w F/U
Potential subjects identified, fitting inclusion/exclusion criteria, by PI from customer database	X							
PI calls potential subjects and pre-screens by telephone	X							
Subject signs ICF, randomization		X	X					
Fitting, Training		X			X			
Subject fills in questionnaires		X		X	X	X	X	X
Subject performs 6MWT w/Borg scale and L-test		X		X	X	X	X	X
PI prints out activity report from investigational device				X			X	X
Subjects that choose to keep using the investigational device are given an appointment in 8-12 weeks from visit 3. Others are fitted with their prescribed prosthesis and end participation.						X	X	

All subjects still active are fitted back to their prescribed prosthesis, end of study.	X
CPO subjects provide feedback on fitting the investigational device	X

For each subject there are three scheduled visits to the study site and questionnaires/tasks/measurements administrated three times during the course of the study, with an additional 4th visit which is optional.

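### The two-sequence crossover is tested with a pooled paired test that has no period term, and the plan does not say which of Group 1's two comparator sessions enters the primary contrast

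*Combined protocol and SAP*

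**What the plan says.** Section 8.1 describes a two-group crossover, and section 8.4 (Visit 1) randomises half of the subjects to each order. In Table 6, Group 1 is tested on the comparator at Visit 1, the device at Visit 2 and the comparator again at Visit 3. Group 2 has no tests at Visit 1, then the comparator at Visit 2 and the device at Visit 3. For Visit 3 the text confirms: "During the third visit all subject will repeat the tests and questionnaires on the prosthesis they are fitted with".

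For the analysis, section 10.1 states that "the hypotheses will be tested using a two-tailed, paired, student's t-test", or the Wilcoxon signed-rank test if the data are not normal. Normality is judged on the outcomes at each timepoint. The section then warns of order effects: "Such effects are: practice, positive carryover effect to the latter condition; and fatigue, negative carryover effect to the latter condition". No analysis provision follows, there or in section 10.3.

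Section 7 defines the comparator mean μ1 for all hypotheses: it "is average of measurements with comparator at 2 weeks". The device mean μ2 is taken at the 2-week follow-up. Neither definition names a visit or a group. Section 8.2 says that subjects give "feedback on their exposure of the comparator at baseline and prior to them being fitted to the investigational device or after", depending on group. Section 8.4 describes Group 1's Visit 1 tests as done "to obtain baseline data".

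Section 8.4 iii also disagrees with itself on the number of sessions. It says "The same functional tests (L-test and 6MWT) will also be carried out at two points in time", while its closing sentence gives three administrations for each subject. Table 6 schedules three for Group 1 and two for Group 2 before the optional visit.

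**The concern.** A single paired test across both groups treats every within-subject difference as having the same mean. If exertion changes from one session to the next for reasons unrelated to the device, the differences move in opposite directions in the two groups. That inflates their variance, and it biases the pooled mean whenever the groups are unequal. The plan recognises such effects but does not remove them, in a study sized at the minimum of 15 completers. Normality is also checked on the wrong quantity, because the paired t-test depends on the differences.

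The unnamed comparator session carries the larger risk. If Visit 1 were used for Group 1, the comparator would come first and the device second in every pair, and randomising the order would protect against nothing. The choice could be made after the data are seen, in an open-label study with a subjective primary endpoint. It also has a practical consequence. Section 10.3 keeps dropouts for the procedures they completed, and a Group 1 subject who leaves after Visit 2 has a pair only through Visit 1. The plan does not say whether that pair counts.

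**Working it through.** **Inputs.** From section 10.2: 15 completers, dz = 0.7084529, α = 0.05, one tail. From section 10.1: a two-tailed paired test. Table 4 states a one-directional alternative for the primary endpoint, so both versions are shown. Assumed, because the documents give no figure: a period effect π of 0.25 to 0.5, in SDs of the paired difference. Positive π means that practice lowers exertion at the later session. Splits are Group 1/Group 2.

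**The plan's own figure.** The effective n is 15 × 3/3.14159 = 14.324. Then δ = 0.7084529 × √14.324 = 2.681, df = 13.324, critical t = 1.768 and power = 0.815. This matches section 10.2.

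**Which visit is μ1 for Group 1?** On the study calendar Group 1 is on the device at 2-3 weeks, so neither of its comparator sessions fits literally. For Group 2, μ2 can only be Visit 3, at 4-6 weeks, so the definitions make sense only as time on the condition. On that reading Group 1's comparator session is Visit 3. No section says so.

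**Visit 3 reading.** Let d = comparator minus device, with SD 1 and true device effect τ. The mean of d is τ − π in Group 1 and τ + π in Group 2.

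- Pooled mean: bias = π(n2 − n1)/n. At 8/7 and π = 0.5 this is 0.5 × (−1)/15 = −0.033.
- Pooled variance: expected s² = 1 + (n1·n2/n)(2π)²/(n − 1) = 1 + (56/15)(1)/14 = 1.267, so the standard error is about 12.5% too large (√1.267 = 1.125).
- Adjusted estimate: the mean of the two group means, SE = ½√(1/n1 + 1/n2) and df = n − 2. At 8/7 the SE is 0.2588, against 1/√15 = 0.2582 for the paired test with no period effect.

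Simulated power at dz = 0.7084529 (400,000 replicates per cell):

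| Split | π | One-sided: pooled | One-sided: adjusted | Two-tailed: pooled | Two-tailed: adjusted |
|---|---|---|---|---|---|
| 8/7 | 0 | 0.832 | 0.828 | 0.723 | 0.716 |
| 8/7 | 0.25 | 0.80 | 0.83 | 0.68 | 0.72 |
| 8/7 | 0.5 | 0.735 | 0.828 | 0.59 | 0.72 |
| 7/8 | 0.25 | 0.83 | 0.83 | 0.72 | 0.72 |
| 7/8 | 0.5 | 0.81 | 0.83 | 0.68 | 0.72 |
| 9/6 | 0 | 0.832 | 0.816 | 0.723 | 0.70 |
| 9/6 | 0.5 | 0.65 | 0.82 | 0.50 | 0.70 |

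For the rank versions at 8/7, π = 0.5, one-sided, signed-rank power is 0.70 and rank-sum power is 0.80 (20,000 replicates).

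One-sided type I error of the pooled test at 8/7 or 7/8 is 0.025-0.051, so it is not inflated. At 6/9 it is 0.066 (π = 0.25) to 0.072 (π = 0.5). Under the two-tailed test the device-favouring tail is then 0.033-0.035, against a nominal 0.025. If fatigue dominates (π negative), the mirrored splits swap roles.

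**Visit 1 reading.** Every pair has mean τ + π, so the bias is π in full. With no device effect and π = 0.25 to 0.5, device-favouring false positives are 0.24-0.58 one-sided and 0.15-0.44 two-tailed. With fatigue of the same size they are 0.005 or less. A period term cannot repair this, because order no longer varies between groups.

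**Unequal prior testing.** On Table 6, Visits 2 and 3 are Group 1's second and third tests but Group 2's first and second. Suppose practice gives a gain q only between the first and second test. Then d has mean 0 in Group 1 and q in Group 2, and the adjusted estimate keeps a bias of (0 + q)/2 = q/2. For an assumed q of 0.25-0.5 SD, its one-sided type I error is 0.12-0.23, and the device-favouring tail of the two-tailed test is 0.065-0.14. Testing both groups at Visit 1 returns the one-sided error to 0.05.

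**The case against.** The best reply is that Visit 3 is the only sensible reading. Visit 1 is labelled baseline throughout and does not follow a 2-week study period on the comparator, while Visit 3 does. The large false-positive rates therefore belong to a reading the plan probably does not intend. On the Visit 3 reading, randomised order balances a common period effect, and near-equal groups leave type I error uninflated. The visible power loss needs π = 0.5, which is about 70% of the planned effect (0.5/0.708). At π = 0.25 and a 7/8 split the pooled test loses nothing. Even at 6/9 the total two-tailed error stays below 0.05 (0.047-0.048 at π = 0.25, 0.041 at π = 0.5). The plateau bias is a scheduling matter: at 8/7 and q = 0.5 the adjusted test has one-sided error 0.233, against 0.201 for the pooled test.

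Most of this stands, and it limits the severity. It does not remove the point. Visit 3 has to be inferred, and section 8.2 cuts across the inference by naming both baseline and a later occasion. Section 10.3 requires deviations from the statistical plan to be approved and reported, but that protects little when the visit is not stated. The power loss is uncertain, whereas the cost of avoiding it is close to nil. The plateau result supports the scheduling remedy only and is not an argument for the period term.

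**Conclusion.** The concern holds and should be fixed, but it does not undermine the design. On the Visit 3 reading with near-equal groups the main cost is power: from nothing to about 0.09 one-sided (0.828 − 0.735) or 0.13 two-tailed (0.72 − 0.59) at 15 completers, for period effects up to 0.5 SD. Uneven completion makes it worse, through a larger power loss at 9/6 or a modest rise in one-sided error at 6/9. The Visit 1 reading would let the whole order effect into the primary comparison. It is the less natural reading, but the text does not exclude it. All these sizes rest on assumed period and practice effects, because the documents give neither their size nor their direction. That the paired test is pooled over both groups is inferred from the single test and from means defined without reference to group.

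**What to change.** 1. State in sections 7 and 10.1 that the primary contrast is Visit 2 versus Visit 3 in both groups, and that Group 1's Visit 1 serves as baseline only. State also that a Group 1 subject without Visit 3 is not paired through Visit 1.
2. Replace the pooled paired test with the two-period crossover analysis. Either compare the Visit 3 minus Visit 2 change between the randomised groups (two-sample t-test, or rank-sum if non-normal; half the difference in group means estimates the device effect), or fit a mixed model with treatment, period and sequence fixed and subject random. Judge normality on those changes. Say plainly that this removes a period effect common to both groups but not differential carryover, which cannot be separated from the device effect here.
3. Reconcile Table 6 with the text of section 8.4 iii on the number of test sessions in each group. Testing Group 2 at Visit 1 would equalise prior exposure and remove the q/2 bias.

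Items 1 and 2 cost wording and one degree of freedom. For the t-test with no period effect, power falls by less than 0.01 at 8/7 and by about 0.02 at 9/6 or 6/9. With the plan's own efficiency correction, the one-sided requirement remains 15 completers. Item 3 costs testing time for about half the subjects, at a visit they already attend.
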